## 11.14 SUSAR reporting

All SUSARs will be reported to the Sponsor, DSMC, relevant Research Ethics Committee and to the MHRA. Fatal or life-threatening SUSARs must be reported within 7 days and all other SUSARs within 15 days. Any additional relevant information should be sent within 8 days of the report.

The CI or Co-Investigator will also inform all Investigators concerned of relevant information about SUSARs that could adversely affect the safety of participants.

## **11.15 Development Safety Update Report**

The CTU (on behalf of the Sponsor) will submit (in addition to the expedited reporting above) Development Safety Update Reports (DSURs) once a year throughout the clinical trial, or on request to the Competent Authority (MHRA in the UK), Ethics Committee, HRA (where required), Host NHS Trust and Sponsor.

The Development International Birth Date (DIBD) for ChAdOx2 CCHF is the date of approval from the MHRA and the data lock point of each DSUR will be the last day of each one-year reporting period.

## 11.16 Safety profile review

The safety profile will undergo review on a day-to-day basis by the Investigators using the electronic diary, adverse events CRF and safety bloods. Any concerns will be referred to the CI. Interim safety reviews will be carried out in Oxford by the CI and at external sites by the CI and local PI via email and/or telephone. If the CI remains concerned, they may consider escalation to the DSMC as required.

## 11.17 Trial Management Group

The CI, lead scientist and study site investigators will form the trial management group (TMG) and will provide on-going management of the trial.

## 11.18 Data Safety Monitoring Committee (DSMC)

For this study, an independent DSMC will be appointed. There will be a minimum of three appropriately qualified committee members of whom one will be the designated Chair. The DSMC will operate in accordance with the trial specific DSMC charter, which will be established before recruitment starts. The Chair of the DSMC may also be contacted for advice where the Chief Investigator feels independent advice or review is required.

## 11.19 Interim safety reviews

## 11.19.1 Sequence of enrolment and study vaccination

Enrolment of Cohort 1: An initial cohort of six participants will be enrolled and receive their first study vaccine prior to the enrolment of further participants. Enrolment will be staggered (Table 10).

Sentinel participant: The first participant enrolled into the trial will be vaccinated alone, ahead of any other participants. Their profile of adverse events will be reviewed for 2 days post-vaccination.

REC Ref: <rec ref=""> IRAS project ID: 1007128 Protocol V2.0, 14th June 2023</rec>	CCHF01: A study of a new vaccine against Crimean-Congo Haemorrhagic Fever (a life- threatening tick-borne viral disease)	Page 53 of 78
---	--	---------------

Participants 2 and 3: Provided there are no safety concerns, as assessed by the CI a further two participants will be vaccinated.

Participants 4, 5 and 6: The accumulated profile of adverse events for first, second and third participants will be reviewed by the CI after two days and if deemed acceptable, the remaining three participants in Cohort 1 will be vaccinated.

Enrolment and study vaccination of Cohort 2: This will occur after a positive decision from the DSMC following the first DSMC safety review (detailed below in section 11.19.3).

Sequence	Participant groups	Minimum interval before next step	Safety review before progression
Step 1	Cohort 1 volunteer 1	2 days	Local safety review by Cl
Step 2	Cohort 1 volunteers 2 and 3	2 days	Local safety review by CI of Cohort 1 volunteers 1, 2 and 3
Step 3	Cohort 1 remaining volunteers	7 days	DSMC review
Step 4	Cohort 2	n/a	n/a
Step 5	6 participants who have a 2 nd dose from either cohort	7 days	Safety review by CI & site PI where appropriate

**Table 11** Sequence of Enrolment for First Doses

## 11.19.2 Sequence of second study vaccine doses

Second study vaccination of Cohort 1 and 2 will be staggered. A second dose of study vaccine will be given to six enrolled participants. The CI and (and where appropriate), PI will conduct a formal safety review of the accumulated safety data from Day 0 to Day 7 following the second study vaccination. This safety dataset will comprise 6 participants who have a 2nd dose from either cohort. If there are no safety concerns, the remaining participants will receive their second dose of study vaccine.

## 11.19.3 DSMC safety reviews

DSMC data review will be done as follows:

 Formal review of the safety profile data after 7 days (Day 0 to Day 7 inclusive) following the first vaccination of all six participants in Cohort 1. This review will decide on progression to enrolling and administering the first dose of vaccine to the remaining participants in the trial (*i.e.* Cohort 2). The review will also decide on progression to administering the second dose of study vaccine to all participants.

REC Ref: <rec ref=""> IRAS project ID: 1007128 Protocol V2.0, 14th June 2023</rec>	CCHF01: A study of a new vaccine against Crimean-Congo Haemorrhagic Fever (a life- threatening tick-borne viral disease)	Page 54 of 78
---	--	---------------

- 2. Formal review of the safety profile, including safety data up to a minimum of 28 days after the second dose of vaccine has been administered to all participants.
- 3. Independent review following any SAE deemed to be related to the trial active vaccine.
- 4. Unscheduled reviews on request of the study management committee at a demand and frequency determined by the severity of reported adverse events.

From these reviews, the DSMC will make recommendations to the study investigators on whether there are any ethical or safety reasons why the trial should not continue. A summary of all AEs and SAEs to date will be provided to the DSMC on request.

The outcome of each DSMC review will be communicated directly to the TMG and documentation of all reviews will be kept in the TMF.

## 11.20 Procedures to be followed in the event of abnormal findings

Laboratory parameters for inclusion/exclusion in the trial will be considered on an individual basis, with investigator discretion for interpretation of results and the need for repeated tests. Abnormal clinical findings from medical history, examination or blood tests will be assessed for clinical significance throughout the trial. If a test is deemed clinically significant, it may be repeated to ensure it is not a single occurrence or spurious result. If a test remains clinically significant, the participant will be informed, and appropriate medical care arranged as appropriate, with the permission of the participant. Decisions to exclude the participant from enrolling in the trial or to withdraw a participant from the trial will be at the discretion of the Investigator.

## 11.21 Safety holding rules

## 11.21.1 Group holding rules

If two or more of the participants in either cohort develop the same unacceptable adverse reaction then study vaccination will be paused pending a DSMC review.

An unacceptable adverse reaction is an adverse event (solicited or unsolicited) occurring within two days after a dose of study vaccination that is severe, with severity lasting at Grade 3 or more for more than 48 hours, and in the opinion of the Chief Investigator and in the opinion of the treating investigator is considered possibly, probably or definitely related to the study vaccination. The treating investigator's assessment of relatedness will not be downgraded by another member of the research study team. Adverse events occurring after study vaccination that meet these criteria but have a plausible alternative causality will not trigger the holding rule.

## • Solicited local Adverse Events:

- o if ≥2 participants in either cohort experience the same Grade 3 solicited local adverse event beginning within 2 days after vaccination (day of vaccination D0 and one subsequent day D1) and persisting at Grade 3 for >48 hrs.
- Solicited systemic Adverse Events:
  - o if ≥2 participants in either cohort experience the same Grade 3 solicited systemic adverse event beginning within 2 days after vaccination (on the day of vaccination [D0 or V2] or on the subsequent day [D1 or V2+1]) and persisting at Grade 3 for >48 hrs.
- Unsolicited Adverse Events:

- o if ≥2 participants in either cohort experience the same Grade 3 unsolicited adverse event (including the same laboratory adverse event) that is considered possibly, probably or definitely related to vaccination and persists at Grade 3 for >48hrs.
- A serious adverse event considered possibly, probably or definitely related to vaccination occurs.
- Death occurs.
- A life-threatening reaction occurs.

If a holding rule has been met and following a safety review by the DSMC it is deemed appropriate to restart dosing. A resumption of dosing can only take place after the regulatory authority approves a substantial amendment application in which with pertinent data is presented.

The DSMC safety review will consider:

- The relationship of the AE or SAE to the vaccine.
- The relationship of the AE or SAE to the vaccine dose, or other possible causes of the event.
- New, relevant safety information from ongoing research programs on the various components of the vaccine.

The DSMC will not downgrade the assessment of an investigator from related to unrelated.

The local ethics committee, MHRA and vaccine manufacturers will also be notified if a holding rule is activated or released.

All vaccinated participants will be followed for safety until the end of their planned participation in the study or until resolution or stabilisation (if determined to be chronic sequelae) of their AEs, providing they consent to this.

In addition to these pre-defined criteria, the study can be put on hold upon advice of the DSMC, CI, Study Sponsor, Regulatory Authority or Ethical Committee(s), for any single event or combination of multiple events which they deem jeopardise the safety of the volunteers or the reliability of the data.

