# 6 OBJECTIVES AND ENDPOINTS

# 6.1 Objectives, outcome measures and evaluation timepoints

Outcome	Objective	Outcome measure	Evaluation timepoints 
Primary	To assess the safety and tolerability of ChAdOx2 CCHF in healthy volunteers	
 
a) Occurrence of solicited local reactogenicity signs and symptoms
 
b) Occurrence of solicited systemic reactogenicity signs and symptoms
 
c) Occurrence of unsolicited adverse events (AEs)
 
d) Occurrence of abnormal safety laboratory measures
 
e) Occurrence of serious adverse events (SAEs) and adverse events
 
	7 days following each vaccination (D0 to D7; V2 to V2+7) 7 days following each vaccination
Secondary		of special interest (AESIs) Anti-CCHF glycoprotein specific serological response	Cohort 1 : D0, D28, V2, V2+28 Cohort 2 : D0, D28, V2, V2+28
	To compare the	Anti-CCHF glycoprotein specific serological response	Cohort 1 : D0, D28, V2, V2+28 Cohort 2 : D0, D28, V2, V2+28
Exploratory 	immunogenicity of ChAdOx2 CCHF vaccine in	a) Anti-CCHF glycoprotein specific serological response	Cohort 1 : D14, D56, V2+14, V2+56, V2+140, V2+280 Cohort 2 : D1, D14, V2+1, V2+14, V2+140, V2+280
		b) CCHF glycoprotein T cell response measured by IFN-γ ELISPOT	Cohort 1 : D0, D14, D28, D56, V2, V2+14, V2+28, V2+56, V2+140, V2+280 Cohort 2 : D0, D1, D14, D28, V2, V2+1, V2+14, V2+28, V2+140, V2+280
	-	a) Anti-CCHF glycoprotein specific serological response	Cohort 1 : D14, D56, V2+14, V2+56, V2+140, V2+280 Cohort 2 : D1, D14, V2+1, V2+14, V2+140, V2+280

individuals previously vaccinated with a ChAdOx vaccine with ChAdOx naïve individuals	b) CCHF glycoprotein T cell response measured by IFN-γ ELISPOT	Cohort 1 : D0, D14, D28, D56, V2, V2+14, V2+28, V2+56, V2+140, V2+280 Cohort 2 : D0, D1, D14, D28, V2, V2+1, V2+14, V2+28, V2+140, V2+280
Immunological profiling	
 
a) CCHF virus neutralising antibodies (using pseudoneutralization assays)
 
b) Cellular immune response to CCHF virus measured by ICS, proliferation and/or whole blood assays
 
c) Further immunological profiling
 
	Timepoints will be detailed in the laboratory analysis plan
To assess anti-vector immunity following vaccination	Binding and/or neutralising antibody responses against ChAdOx1	Timepoints will be detailed in the laboratory analysis plan

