## 11.21.2 Individual holding rules

In addition to the above stated group holding rule, stopping rules for individual participants will apply (*i.e.*, indications to withdraw individuals from further vaccinations) where the event is considered clinically significant by the investigator:

- Local reactions: the participant develops injection site ulceration, abscess or necrosis.
- Systemic solicited adverse events: the participant develops a Grade 3 systemic solicited adverse event considered possibly, probably, or definitely related to vaccination within 2 days after vaccination (on the day of vaccination [D0 or V2] or on the subsequent day [D1 or V2+1]) and persisting at Grade 3 for >48hrs.
- **Laboratory AEs**: the participant develops a Grade 3 laboratory adverse event considered possibly, probably, or definitely related to vaccination within 7 days after vaccination and persisting at Grade 3 for > 7 days (laboratory AE reference ranges are shown in Appendix E).
- Unsolicited adverse events:
  - The participant has a Grade 3 adverse event considered possibly, probably, or definitely related to vaccination, persisting at Grade 3 for >48hrs.

- The participant has a serious adverse event considered possibly, probably or definitely related to vaccination.
- The participant has an acute allergic reaction or anaphylactic shock following the administration of an investigational product.

If a participant fulfils any of the temporary exclusion criteria at the scheduled time of a second administration of investigational product, the participant will not receive the vaccine at that time. The vaccine may be administered to that volunteer at a later date within the time window specified in the protocol or they may be withdrawn from the study at the discretion of the Investigator.

All vaccinated participants will be followed for safety until the end of their planned participation in the study or until resolution or stabilisation (if determined to be chronic sequelae) of their AEs, providing they consent to this.

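### Group holding rule (11.21.1): the solicited local bullet names first-dose days only, the systemic bullet names both doses, the lead paragraph adds a causality test, and nothing says which governs

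*Protocol*

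**What the plan says.** Section 11.21.1 of the protocol has two layers.

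**Lead paragraph.** It carries its own trigger, with a committee review to follow: "If two or more of the participants in either cohort develop the same unacceptable adverse reaction then study vaccination will be paused pending a DSMC". The definition that follows is broad on type of event, "An unacceptable adverse reaction is an adverse event (solicited or unsolicited"), and on dose, "occurring within two days after a dose of study vaccination that is severe". The event must stay at Grade 3 or above for over 48 hours, and the Chief Investigator and the treating investigator must consider it at least possibly related. The paragraph ends by excluding events that have a plausible alternative cause.

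**Bullets.** Each is a separate condition by type of event.
- Solicited local, Grade 3 for more than 48 hours, two or more participants: "beginning within 2 days after vaccination (day of vaccination D0 and one subsequent day D1".
- Solicited systemic, same grade, duration and count: "on the day of vaccination [D0 or V2] or on the subsequent day [D1 or V2+1".
- Unsolicited, same grade, duration and count: relatedness is required in the bullet itself, and there is no onset limit.

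Neither solicited bullet mentions relatedness.

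**Day labels.** Section 6.1 separates the doses: "7 days following each vaccination (D0 to D7; V2 to V2+7". The schedules in 4.2 and 4.3 do the same, with D0 as the first vaccination visit and V2 as the second. The individual systemic rule in 11.21.2 also uses the two-dose labels.

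**The concern.** Two neighbouring bullets of one safety rule use different day notation. Taken at its word, the local bullet applies to the first dose and the systemic bullet to both. The lead paragraph does reach local reactions after dose 2, but by a different test, and the section gives no order of precedence.

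Whether a holding rule has been met should not depend on which line is read. Once one is met, dosing can restart only after a DSMC review and regulatory approval of a substantial amendment, and the ethics committee, the MHRA and the manufacturers are notified. An error in either direction is therefore costly: a pause that should have happened is missed, or a formal halt is declared that the text may not require. Cohort 2 may be recruited at more than one site, so different staff will apply the wording. Solicited local reactogenicity is also the first listed primary outcome in section 6.1.

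**Working it through.** The protocol gives no trigger probability or other figure on this point, so the check is a comparison of texts.

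**Step 1: what the labels mean.** Sections 4.2, 4.3 and 6.1 use D for days from the first dose and V2 for days from the second. On that notation, D0 and D1 in the local bullet are first-dose days.

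**Step 2: are the bullets just restatements of the lead paragraph?** The text does not support that cleanly. The unsolicited bullet drops the two-day onset limit that the lead paragraph sets, so it is not a restatement. It also repeats the relatedness condition, which the two solicited bullets leave out. That pattern suggests separate triggers, but the section does not say so.

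**Step 3: apply each reading to one case.** Take two participants with the same Grade 3 local reaction, starting on the vaccination day or the next day and lasting more than 48 hours, where the lead paragraph's causality conditions are *not* met.

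| Reading of 11.21.1 | After dose 1 | After dose 2 |
|---|---|---|
| Bullets are separate triggers, local bullet read literally (D0, D1) | Pause | No pause |
| Bullets are separate triggers, local bracket read as a day count from either dose | Pause | Pause |
| Bullets only illustrate the lead paragraph, whose conditions apply throughout | No pause | No pause |

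If the causality conditions *are* met, every cell becomes a pause, because the lead paragraph is then satisfied whatever the dose.

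**Step 4: how often would the readings differ?** Only when the lead paragraph's conditions fail, and that bar is low. Under section 11.3 a reasonable temporal relationship is enough on its own for an event to count as possibly related, and onset within a day of vaccination makes that easy to satisfy. The lead paragraph also says that a treating investigator's finding of relatedness may not be downgraded by others in the study team. What is left is a treating investigator who judges the event unrelated, or the exclusion for a plausible alternative cause.

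**Step 5: when would it matter?** Under 11.19.2, six participants receive a second dose and are reviewed before the rest, so up to 46 − 6 = 40 second doses follow that review. The next scheduled DSMC review in 11.19.3 needs at least 28 days of data after everyone's second dose. The 40 describes the period in which the wording could be tested. It does not count doses that lack a rule.

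**The case against.** The strongest reply is that nothing is uncovered. The lead paragraph is itself a pause trigger, does not except local events, and applies after any dose. The local bullet opens with general words about time since vaccination, so its bracket may be no more than a day count. The protocol elsewhere counts days from either dose: 11.19.2 speaks of Day 0 to Day 7 after the second vaccination, and 11.8 counts days after each vaccine. Other brakes also remain, namely the triggers for related serious events, deaths and life-threatening reactions, the power to hold for any single event, automatic alerts for Grade 3 diary entries, and day-to-day safety review.

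Most of this stands. It limits the finding to an inconsistency of wording and makes a drafting slip the likely explanation. It does not settle the matter, because the next bullet in the same list spells out both doses and the lead paragraph sets conditions that the solicited bullets lack.

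A reader might go on to infer that the individual rule in 11.21.2 is also faulty, since its only local criterion is "Local reactions: the participant develops injection site ulceration, abscess or necrosis", whereas "Systemic solicited adverse events: the participant develops a Grade 3 systemic solicited adverse event" opens a criterion based on persistence at Grade 3. The documents do not support that. A different criterion for local reactions is not a contradiction. A group pause stops dosing for everyone, including those affected. Sections 8.2 and 9.8 allow a further vaccination to be deferred or discontinued for an adverse event, and every individual criterion depends on the investigator finding the event clinically significant.

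**Conclusion.** The point holds as an internal inconsistency in a safety decision rule. As written, two persistent Grade 3 local reactions of the same kind pause vaccination outright after dose 1, but after dose 2 only if they pass the lead paragraph's causality test, and the section does not say which text governs.

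Its practical size is small and cannot be quantified from the protocol. The readings differ only when relatedness is denied or a plausible alternative cause is accepted. A reader might infer that local reactions after dose 2 have no pause rule at all, or that the holding rule is the only safeguard once second doses are released. Neither follows: the lead paragraph reaches those reactions, and the other triggers and hold powers in 11.21.1 remain in force.

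The conclusion assumes that D0 and V2 carry the meaning they have in 4.2, 4.3 and 6.1, and that the bullets can operate as separate triggers. If the sponsor intended otherwise, the text needs to say so.

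**What to change.** Reconcile the lead paragraph of 11.21.1 with its bullets.

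1. Write the onset window of the solicited local bullet in the same day notation as the systemic bullet, so that the doses it covers are explicit.
2. State whether the lead paragraph's conditions (relatedness, and no plausible alternative cause) apply to the two solicited bullets, or whether those bullets trigger a pause on their own.

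Which doses and which causality conditions should apply is a clinical decision for the investigators and the DSMC. The request is only that the section give one answer.

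The cost is a wording change within a protocol amendment. One small downside: if the local bullet is confirmed to cover both doses, a pause becomes slightly more likely during dose 2.

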## 11.21.2 Individual holding rules

In addition to the above stated group holding rule, stopping rules for individual participants will apply (*i.e.*, indications to withdraw individuals from further vaccinations) where the event is considered clinically significant by the investigator:

- Local reactions: the participant develops injection site ulceration, abscess or necrosis.
- Systemic solicited adverse events: the participant develops a Grade 3 systemic solicited adverse event considered possibly, probably, or definitely related to vaccination within 2 days after vaccination (on the day of vaccination [D0 or V2] or on the subsequent day [D1 or V2+1]) and persisting at Grade 3 for >48hrs.
- **Laboratory AEs**: the participant develops a Grade 3 laboratory adverse event considered possibly, probably, or definitely related to vaccination within 7 days after vaccination and persisting at Grade 3 for > 7 days (laboratory AE reference ranges are shown in Appendix E).
- Unsolicited adverse events:
  - The participant has a Grade 3 adverse event considered possibly, probably, or definitely related to vaccination, persisting at Grade 3 for >48hrs.

- The participant has a serious adverse event considered possibly, probably or definitely related to vaccination.
- The participant has an acute allergic reaction or anaphylactic shock following the administration of an investigational product.

If a participant fulfils any of the temporary exclusion criteria at the scheduled time of a second administration of investigational product, the participant will not receive the vaccine at that time. The vaccine may be administered to that volunteer at a later date within the time window specified in the protocol or they may be withdrawn from the study at the discretion of the Investigator.

All vaccinated participants will be followed for safety until the end of their planned participation in the study or until resolution or stabilisation (if determined to be chronic sequelae) of their AEs, providing they consent to this.

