#### 4.3 Schedule of procedures table: Vaccination and follow up visits (Cohort 2)

Table 3 Schedule Visit Number	1	2 2	3	4	5	6	101 ( Z) 7	8	9	10
Visit type	- Vac1	f/u	f/u	f/u	Vac2	f/u	f/u	f/u	f/u	f/u
			-	-		V2	V2	V2	V2	V2
Timeline 	D0	D1	D14	D28	V2 (D84)	+1	+14	+28	+140	+280
Time window (days)		±0	±3	±3	±14	±0	±3	±3	±28	±60
Visit Procedures										
Review contraindications, inclusion and exclusion criteria	Х				x					
Vaccination	Х				Х					
Vital signs (heart rate, temperature, blood pressure)	х	х	х	х	х	х	х	х		
Targeted medical history/physical examination, if required	(X)	(X)	(X)	(X)	(X)	(X)	(X)	(X)	(X)	(X)
Adverse Event Collection										
Solicited AE collection	D0 t	o D7			V2 to	V2+7				
Unsolicited AE collection	I	D0 to D28		V2 to V2+28						
SAEs & AESI collection	Х	Х	Х	Х	Х	Х	Х	Х	Х	Х
Review ongoing AEs		Х	х	Х	Х	Х	х	Х	Х	Х
Electronic diary (eDiary) 										
Electronic diary started	Х				Х					
Electronic diary review (in clinic)		х	Х	х		х	х	х		
Electronic diary closed				Х				х		
Urine Samples										
High sensitivity Urinary hCG ( P OCBP only)	Х				x					х
Stool samples [optional]										
Home collection of stool samples 	[X]		[X]				[X]			[X]
Blood Samples 										
HLA typing (mL)	~4									
Biochemistry, Haematology (mL) [LFTs, U+Es, FBC]	~5	~5	~5	~5	~5	~5	~5	~5	~5	~5
Immunology (mL)	~50	~30	~50	~50	~50	~30	~50	~70	~50	~50
PAXgene (ml)	~2.5	~2.5			~2.5	~2.5				
Blood volume per visit (mL)	~61.5	~37.5	~55	~55	~57.5	~37.5	~55	~75	~55	~55
Cumulative blood volume (mL)	71.5	109	164	219	276.5	314	369	444	499	554

**Table 3** Schedule of procedures: Vaccination and follow up visits (Cohort 2)

Additional unscheduled visits may occur (for example: to repeat a blood test, for additional clinical review)

REC Ref: <rec REF> IRAS project ID: 1007128 Protocol V2.0, 14th June 2023

CCHF01: A study of a new vaccine against Crimean-Congo Haemorrhagic Fever (a lifethreatening tick-borne viral disease) Page 11 of 78

eDiaries are remotely monitored in (near) real-time for the occurrence of grade  $\geq$ 3 AEs and daily for non-completion

Minor differences in blood volumes may occur depending on the collection tubes and equipment used (~ = approximately); additional repeat blood draws may be required (for example, if there is a problem with the sample, result abnormality, or participant unwell)

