REC Ref: <rec ref=""> IRAS project ID: 1007128 Protocol V2.0, 14th June 2023</rec>	CCHF01: A study of a new vaccine against Crimean-Congo Haemorrhagic Fever (a life- threatening tick-borne viral disease)	Page 26 of 78
---	--	---------------

A review of 170 definite and 50 probable cases of VITT in the UK found a case mortality rate of 22%. Most cases occurred between 5 and 30 days after vaccination (median 14 days, maximum 48 days). The age range was 18 to 79 years (median, 48), with no sex preponderance and no identifiable medical risk factors. Another UK study of over 3.7 million recipients of ChAdOx1 nCoV-19 found that after the first dose there was an increased risk of venous thromboembolism (standardized incidence ratio: 1.12 [95% CI: 1.05 to 1.20]), and of cerebral venous sinus thrombosis (standardized incidence ratio: 4.14 [95% CI: 2.54 to 6.76]). Up to 23 November 2022, the MHRA had received Yellow Card reports of 445 cases of major thromboembolic events with concurrent thrombocytopenia in the UK following vaccination with ChAdOx1 nCoV-19 (221 in females, and 219 in males; age range from 18 to 93 years). Fifty-one of the 445 reports have been reported after a second dose. The overall case fatality rate was 18% with 81 deaths, six of which occurred after the second dose. Cerebral venous sinus thrombosis was reported in 161 cases (average age 46 years) and 284 had other major thromboembolic events (average age 54 years) with concurrent thrombocytopenia. The estimated number of first doses of COVID-19 Vaccine AstraZeneca administered in the UK by 23 November 2022 was 24.9 million and the estimated number of second doses was 24.1 million. The reported incidence of major thromboembolic events with concurrent thrombocytopenia following the first dose was higher in the younger adult age groups compared to the older groups (21.8 per million doses in those aged 18-49 years compared to 11.3 per million doses in those aged 50 years and over). This contrasts with incidence of these events after the second dose, which were commoner in the older age group (1.0 per million doses in those aged 18-49 years compared to 2.1 per million doses in those aged 50 years and over).

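### The holding rules disagree on whether a related Grade 3 laboratory event that begins after the first days can trigger a pre-defined hold

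*Protocol*

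**What the plan says.** **Group rules (11.21.1).** Vaccination pauses for DSMC review if two or more participants develop the same unacceptable reaction. The definition reads: "An unacceptable adverse reaction is an adverse event (solicited or unsolicited) occurring within two days after a dose of study vaccination that is severe". It adds that Grade 3 or more must last over 48 hours. Bullets follow. The two solicited bullets repeat the two-day limit, and the local one explains it as "day of vaccination D0 and one subsequent day D1". The unsolicited bullet also needs two participants with the same Grade 3 event, "including the same laboratory adverse event) that is considered possibly, probably or definitely related to vaccination and persists at Grade 3 for >48hrs". It gives no onset limit.

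**Individual rules (11.21.2).** These decide who receives no further vaccine, and apply "where the event is considered clinically significant by the investigator". The laboratory bullet covers a Grade 3 laboratory event "considered possibly, probably, or definitely related to vaccination within 7 days after vaccination and persisting at Grade 3 for > 7 days". The unsolicited bullet reads: "The participant has a Grade 3 adverse event considered possibly, probably, or definitely related to vaccination, persisting at Grade 3 for >48hrs". It has no onset limit and does not exclude laboratory events.

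**Neighbouring text.** Section 11.8 describes unsolicited events as those found by open questioning, and sets SAEs and AESIs apart from them. Laboratory events have their own section, 11.10, where Grade 4 counts as an SAE. Both schedules (4.2 and 4.3) list the safety panel, in Cohort 2 as "Biochemistry, Haematology (mL) [LFTs, U+Es, FBC", at every visit.

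**The concern.** A pre-defined holding rule should give the same answer whoever applies it. Here the answer for a Grade 3 laboratory event depends on which sentence is read.

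Timing makes this more than a drafting matter. For the closest licensed vaccine, section 5.9.1 says of VITT: "Most cases occurred between 5 and 30 days after vaccination (median 14 days, maximum 48 days". Laboratory signals with that timing would be found mainly at the D14 and D28 panels, which are the ones the onset limits affect.

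No scheduled DSMC review covers those panels before dose 2. Under 11.19.3 the first review uses D0 to D7 of Cohort 1 and also decides on dose 2 for everyone. The next uses data to at least 28 days after dose 2 in all participants.

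An error in either direction is costly. A missed hold lets dose 2 proceed without the intended review. An unintended hold can be lifted only after the regulator approves a substantial amendment (11.21.1).

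**Working it through.** **1. One case under each text.** Take a related ALT of 5.1 to 10 times the upper limit of normal (Grade 3, Appendix E). It is below Grade 3 at D7, is found at D14 and stays at Grade 3 for five days. ALT is a cleaner example than platelets, because thrombocytopenia is a listed AESI and 11.8 sets AESIs apart from unsolicited events.

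| Text | Onset limit | Duration at Grade 3 | Result |
|---|---|---|---|
| 11.21.1 definition | 2 days | >48 h | Two such participants: no pause |
| 11.21.1 unsolicited bullet | none | >48 h | Two such participants: pause |
| 11.21.2 laboratory bullet | 7 days | >7 days | Participant not stopped |
| 11.21.2 unsolicited bullet | none | >48 h | Participant stopped, if laboratory events count as unsolicited and the event is judged clinically significant |

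Rows 1 and 2 belong to the same rule and contradict each other. Rows 3 and 4 differ only if laboratory events are unsolicited: the group bullet says they are, while 11.8 suggests they are not.

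**2. Check of the inputs.** The Synopsis gives 46 participants, and 6 + 40 = 46. Summing the visit blood volumes in 4.2 and 4.3 with the 10 mL at screening gives 10 + 594 = 604 mL (Cohort 1) and 10 + 544 = 554 mL (Cohort 2), as stated. The schedule rows, including the 5 mL safety panel at each visit, are therefore read correctly.

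**3. Scheduled panels after dose 1, up to D28.**
- Cohort 1: D2, D7, D14, D28, so 6 × 4 = 24.
- Cohort 2: D1, D14, D28, so 40 × 3 = 120.
- Total: 24 + 120 = 144.
- At D14 or D28: 6 × 2 + 40 × 2 = 12 + 80 = 92, and 92/144 = 63.9%.

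**4. Panels whose nominal day falls inside each onset limit.**
- Two days, read as D0 and D1: 40/144 = 27.8%. If day 2 also counts: 40 + 6 = 46, or 31.9%.
- Seven days: 40 (D1) + 6 (D2) + 6 (D7) = 52, or 36.1%.
- No limit: 144, or 100%.

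**5. Day found is not day of onset.** Cohort 2 has no scheduled panel between D1 and D14 ± 3, a gap of 10 to 16 days. A Grade 3 value first found at its D14 visit could have begun within seven days. So 40 of the 92 panels cannot be placed on either side of the seven-day limit. The other 92 − 40 = 52 (Cohort 1 at D14, 6; both cohorts at D28, 46) lie beyond it on the nominal schedule if the preceding panel was below Grade 3. The same gap means that a Cohort 2 D14 panel can show more than seven days' persistence of a value first seen at D1.

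**The case against.** **The later panels can stop dosing anyway.** This stands. A reader might infer from the onset limits that D14 and D28 results cannot stop any dosing, and the document does not support that. A Grade 4 value is an SAE, and a related SAE triggers both rule sets. Section 8.2 item 5 postpones dose 2 for a laboratory event that needs time or investigation. Section 9.8 allows the investigator to withdraw a participant. Section 11.21.1 ends with a discretionary hold for any event, and 11.19.3 allows unscheduled DSMC reviews. A D14 panel can also complete the laboratory rule for an earlier value. These routes rest on judgement or a higher grade, so they do not settle what the pre-defined Grade 3 rule is.

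**Group and individual rules may differ.** This also stands. A reader might count three onset limits and two durations across the section and call that the contradiction. But 11.21.2 applies in addition to the group rule, and pausing a trial and stopping one person may properly use different criteria. The conflict lies within each level.

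**In 11.21.2 the specific bullet governs.** This is a reasonable reading, helped by 11.8 and 11.10. Against it, 11.21.1 expressly places laboratory events among the unsolicited ones, and nothing in 11.21.2 excludes them. This half of the point is therefore conditional.

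**The 11.21.1 bullets are not bound by the definition.** Related SAEs, death and life-threatening reactions are listed without a two-day limit. But those are single-event triggers. The unsolicited bullet needs two participants, the same event and over 48 hours, just as the definition does. The definition names unsolicited events, so the text does not show which prevails.

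**Oversight would prevent inconsistent use.** Chief investigator involvement and weekly cross-site meetings (11.16, 15.6) reduce the risk that the two recruiting sites diverge. They do not say which reading is correct.

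**Conclusion.** The concern holds in limited form. Section 11.21.1 contradicts itself on whether a related Grade 3 laboratory event with onset after two days can pause the trial. Section 11.21.2 gives two answers for one participant if laboratory events count as unsolicited, which the protocol supports in one place and not in another.

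On the nominal schedule, 92 of 144 post-dose-1 panels up to D28 (64%) fall on days where the reading matters. For 40 of them (Cohort 2, D14) true onset is unobserved. The protocol gives no rate of Grade 3 laboratory events, so the panel count is not an estimate of participants affected or of holds missed.

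A reader might also infer that Grade 3 platelets (25–99) first found at D14 or D28 are unprotected. That goes too far. They need not be an SAE by grade and no holding rule names AESIs, but the unsolicited bullets may catch them, non-serious AESIs go into DSMC reports (11.2), and the discretionary routes remain.

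This should be clarified because it bears on dose 2. It does not leave participants without protection.

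**What to change.** **In 11.21.1**, after the definition, add: *The two-day onset limit applies to solicited events only; unsolicited and laboratory events count whenever they begin.* This resolves the contradiction in the safer direction.

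**In 11.21.2**, state which single bullet governs laboratory events. If it is the laboratory bullet, exclude laboratory events from the unsolicited bullet. Also say how onset is dated when a Grade 3 value is first found at D14 in Cohort 2, for example: *treated as within 7 days unless an earlier panel shows otherwise.*

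**Optional, for the sponsor:** changing the individual laboratory duration from over 7 days to over 48 hours. That would set a new individual threshold. A participant whose Grade 3 value lasts 3 to 7 days might then lose dose 2, and some Grade 3 bands are narrow (potassium 5.5–5.6 mmol/L). The clinical-significance condition would limit this. The conflict can be resolved without it.

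**Cost:** a few sentences. Showing persistence may need a repeat draw of about 5 mL, which the schedule footnotes already allow. The downside is that late laboratory events may pause the trial somewhat more often, and each pause needs an approved substantial amendment to lift.
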